Update, January 2025: Since the initial award, and based on challenges navigating the COVID-19 pandemic to recruit participants and complete study visits, we received approval from the sponsor to transition the randomized control trial (Aim 3) to a feasibility study with a smaller sample size. In the feasibility study for Aim 3, we aimed to recruit n=30 participants and understand the feasibility of scaling this study at a larger size and understand the challenges of implementing this intervention with this population of adults experiencing suicide, self-injury, and substance use. The rest of the study design, aside from the sample size in Aim 3, remained the same throughout the project.

- B. Provide a sample size and a justification as to how you arrived at that number. If you use screening procedures to arrive at a final sample a table may be helpful.
 - Aim 1: We anticipate conducting free-listing, key informant interviews with approximately 30 respondents. This sample size is based on considerations in qualitative research theory regarding saturation, a point after which common themes and information from local respondents tend to converge.
 - Aim 2: We estimate having 8 team members (plus the PI) trained in the intervention and piloting the intervention with 8 non-research participants.

Aim 3: For the RCT, estimated Sample Size is N=100 across the two groups Sample size for this aim is based on powering our sample to detect clinically meaningful and statistically significant difference in posttraumatic stress symptoms (primary outcome) between the two groups at 6-month (24wks) post baseline (12wks intervention period; 12wk assessment period). With power set to 80% and the type-I error rate set to alpha = 0.05, with a minimum of three time points and assuming a correlation of 0.3 between timepoints, we would expect to need a total sample size of N=70 to detect a medium effect of (f=0.25). We further adjusted our sample sizes to account for a conservative estimate of 30% attrition based on previous common elements RCTs, which yielded a total sample size of N=100 across the two groups.

In the updated feasibility study for Aim 3, we aimed to recruit a sample size of N=30 participants, which was an achievable goal for the study timeline based on recruitment patterns post-COVID. It

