Aim 3 (RCT): Our main analysis will be done on the "intent-to-treat" sample. This study utilizes repeated measures which leads to a nested data structure: 5 repeated assessments (level-1), nested within individuals (level-2), and nested within providers (level-3). We will use mixed-effects regression models (MRMs), which accommodate variability in assessment number and spacing within and across participants, continuous and discrete outcomes, and varied patterns of change over time (e.g., quadratic). 41 Model Building & Estimation. Outcomes will be graphically and descriptively evaluated to determine the best distribution for modeling using "spaghetti plots" and boxplots of outcome scores at each time-point. We will compare the within subjects covariance structure using model comparison techniques, selecting the appropriate covariance structure based on model fit (AIC, BIC). Then, we will build our models using the approach described in Singer and Willett: 42 1) Model 1 will estimate the proportion of outcome variance at each level specified above; 2) Model 2 will add growth terms (linear, quadratic) to examine how scores on outcomes change over time; 3) Model 3 will add fixed-effect indicators to test for differences in outcomes by baseline characteristic (gender, age). 4) Model 4 will add intervention (0=Control; 1=My Pathway to Healing) and condition by time interaction terms. Intervention effects will be the difference in outcome scores over time between the two groups.

In the feasibility study for Aim 3, we adapted the analysis plan to better understand the context, study population, and goals of the intervention for scaling and implementation. The feasibility analysis plan involves reviewing the notes from weekly study progress calls regarding challenges and successes in implementing the intervention in this sample of participants in this setting, and case manager responses to similar prompts in the intervention and assessment data collection in REDCap. Case managers have provided additional insights into the feasibility of implementing and scaling when giving feedback on the study progress and preliminary findings.

Study Participants:

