Session summary forms: One for intervention participants and one for control participants, these forms are used to track the mental health and well-being of study participants on a week-to-week basis. The forms ask questions about details of the control/intervention visits, including when they took place, what (if any) referrals were made, potential adverse events reported, interruptions during the visit, etc. The intervention form also asks about which parts of the MP2H curriculum were delivered.

Participant monitoring form is a brief form administered at each session of the My Pathway to Healing intervention that assesses for symptoms of depression, anxiety, trauma substance misuse, and safety. This form informs adaptations and tailoring of the intervention content and can help those delivering the intervention in identifying risk.

5. Answer the following if they are relevant to your study design:

A. If the study has different arms, explain the process for assigning participants (intervention/control, case/control), including the sequence and timing of the assignment.

The study has different arms only for Aim 3. There will be an intervention (My Pathways to Healing) group and a control group. Eligible, participants will be block randomized by index event (suicide attempt, suicide ideation, self-injurious behavior, or binge substance use) and gender using a 1:1 allocation ratio within blocks to either receive My Pathway to Healing immediately or be asked to wait. Randomization will occur after informed consent to participate in the study and the baseline assessment has been completed. At that point, the Research Program Assistant will tell the participant that a person from the team will be in touch about either starting My Pathway to Healing or scheduling a next assessment visit. The study coordinator will then check the data and if assigned to My Pathway to Healing, facilitate the referral to one of the community mental health specialists, based on who has availability in their schedule and is in close proximity to where the participant lives. If assigned to the wait-control group, the Research Program Assistant will schedule the next assessment visit with the participant through a follow-up call or visit.

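### Model 4 gives the arms separate baseline means and never uses the baseline score, so a between-arm estimate gives up precision that costs nothing to recover (no bias is involved)

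*Combined protocol and SAP*

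**What the plan says.** Section V.C.4 (Aim 3) sets up a mixed-effects model with five repeated assessments at level 1. Section V.C.2 shows that baseline is one of the five; the others are endline and 4, 8 and 12 weeks after endline.

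The model is built in steps. Growth terms (linear, quadratic) enter in Model 2. Then "Model 3 will add fixed-effect indicators to test for differences in outcomes by baseline characteristic (gender, age" closes the list of baseline covariates. Then "Model 4 will add intervention (0=Control; 1=My Pathway to Healing) and condition by time interaction terms". The effect is defined in one sentence: "Intervention effects will be the difference in outcome scores over time between the two groups". A baseline-score covariate or a common baseline mean is mentioned nowhere.

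Section V.C.5.A places randomisation after consent and the completed baseline assessment, "using a 1:1 allocation ratio within blocks".

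Section III.B names the between-group difference in post-traumatic stress symptoms 24 weeks after baseline as the target. It sizes the trial "assuming a correlation of 0.3 between timepoints".

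The last paragraph on Aim 3 analysis in Section V.C.4 says that the plan was adapted for the feasibility study (N=30) to a review of call notes and case manager responses. The January 2025 update in Section III.A says that the design is otherwise unchanged.

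**The concern.** Because allocation comes after the baseline measurement, any baseline difference between arms is chance. A model with an unrestricted intervention term at time 0 spends information on estimating a quantity known to be zero in expectation.

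If the effect is then read from the condition-by-time terms, it is a comparison of change from baseline, and the whole of the baseline noise is subtracted from the follow-up score. With a low correlation between visits, which is what the plan assumes, that subtraction adds more noise than it removes. What is at stake is the width of the interval for the primary outcome and for the other continuous outcomes measured at baseline.

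**Working it through.** **Inputs.** From Section III.B: correlation 0.3, alpha 0.05, power 80%, at least three time points, f=0.25, N=70, 30% attrition. From Section V.C.5.A: 1:1 allocation. From Section V.C.2: five visits, taken as weeks 0, 12, 16, 20 and 24. Assumed here: compound symmetry, complete data, no provider effect, a two-sided test, and d = 2f = 0.5 for two equal groups.

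**The plan's own figure.** The plan states: "With power set to 80% and the type-I error rate set to alpha = 0.05, with a minimum of three time points", and a "total sample size of N=70 to detect a medium effect of (f=0.25". For a repeated-measures test of arm averaged over m=3 time points, λ = N·f²·m/(1+(m−1)ρ) = 70 × 0.0625 × 3/1.6 = 8.20 on 1 and 68 df, which gives power 0.806. So N=70 reproduces, and 70/0.70 = 100. The within-between interaction version gives N=38, so 70 was not sized on the condition-by-time contrast.

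**Variances of the 24-week effect**, in units of 2σ²/n with n per arm, visit as factor:

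- Change contrast (condition by time): 2(1−ρ) = 2 × 0.7 = 1.40.
- 24-week arm difference from the unmodified Model 4 (main effect plus interaction): 1.00.
- Common baseline mean: 1−ρ² = 1−0.09 = 0.91.

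The excess is 2/(1+ρ) = 1.54 for the change contrast and 1/(1−ρ²) = 1.10 for the 24-week difference.

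**Other time codings at ρ=0.3**, by generalised least squares on the five visits:

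| Time | Change contrast | 24-week difference, unmodified | Common baseline | Ratio, change | Ratio, 24-week |
|---|---|---|---|---|---|
| Visit as factor | 1.40 | 1.00 | 0.91 | 1.54 | 1.10 |
| Linear + quadratic | 1.207 | 0.867 | 0.760 | 1.59 | 1.14 |
| Linear only | 1.189 | 0.630 | 0.603 | 1.97 | 1.05 |

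If endline falls at week 8 (visits at weeks 0, 8, 12, 16 and 20), the linear plus quadratic ratios at the last visit are 1.54 and 1.15, and the linear ratios are 1.84 and 1.04.

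**Dependence on the correlation** (visit as factor, then linear plus quadratic):

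| ρ | Ratio, change | Ratio, 24-week |
|---|---|---|
| 0.3 | 1.54, 1.59 | 1.10, 1.14 |
| 0.5 | 1.33, 1.36 | 1.33, 1.43 |
| 0.7 | 1.18, 1.19 | 1.96, 2.17 |

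The change contrast loses most when correlation is low, and the 24-week difference loses most when it is high. The common-baseline model has the smallest variance in every case.

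**Power and interval width** (d=0.5, visit as factor, ρ=0.3, normal approximation, SE = √(4v/N) in SD units):

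| Estimator | SE, 70 completers | Power, 70 completers | 95% half-width, 21 completers |
|---|---|---|---|
| Change contrast, v=1.40 | 0.283 | 42% | 1.01 SD |
| 24-week difference, unmodified, v=1.00 | 0.239 | 55% | 0.86 SD |
| Common baseline, v=0.91 | 0.228 | 59% | 0.82 SD |

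Here 21 = 30 × 0.70, which applies the plan's 30% attrition to the feasibility sample. The powers are for a single 24-week contrast, so they are not comparable with the plan's 80%, which is for an average over time points.

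**The case against.** **The free baseline is not the whole of the 1.5.** A reader might infer that the unrestricted baseline term by itself inflates the variance by half. The documents do not support that. Section III.B names the 24-week difference as the target, and the sentence in Section V.C.4 about scores over time does not clearly commit to the change contrast. Read as main effect plus interaction, the unmodified model already gives the 24-week difference. At ρ=0.3 most of the gain then comes from that choice (1.40 to 1.00), and the constraint adds the rest (1.00 to 0.91). This objection stands and limits the claim. It does not remove it, because at 0.5 and 0.7 the constraint matters more under this reading.

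**Nothing is wrong with the estimate.** This also stands. Either reading of Model 4 is unbiased and is a recognised growth-model analysis, described under a form heading that asks for a brief plan.

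**The trial is now a feasibility study.** A reader might infer that the loss falls directly on the N=30 results. The feasibility paragraph describes a qualitative review and does not say whether the mixed model will be run. It does not withdraw the model either: the text remains in the current version, the update says the rest of the design is unchanged, and the five assessments remain scheduled. The powers at 70 completers belong to the N=100 plan. At N=30 without losses, the corresponding powers are about 21% and 30%, so neither version supports an efficacy test.

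**The formulas are for continuous scores.** That is correct. The plan allows for discrete outcomes, and the ASSIST yields risk groups, so the ratios do not carry over to every secondary outcome.

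**Conclusion.** The point holds as a free improvement in precision. At the plan's correlation the change contrast carries about 1.5 to 1.6 times the variance of a common-baseline analysis with visit as factor or linear plus quadratic time. If the 24-week difference is read from the unmodified model, the excess is about 1.05 to 1.14 times, rising to 1.3 to 1.4 at a correlation of 0.5 and about 2 at 0.7. The plan leaves open which reading applies.

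These figures rest on compound symmetry, complete data and no provider effect. For the feasibility study the practical consequence is limited to the interval around any between-arm estimate that is reported: a half-width of about 0.82 SD, against 1.01 SD for the change contrast, at 21 completers by normal approximation.

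**What to change.** In Section V.C.4, for any between-arm estimate reported:

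- Code time from baseline. In Model 4 omit the arm difference at time 0, so that the arms share a baseline mean, and keep the condition-by-time terms.
- Define the intervention effect as the fitted arm difference at 24 weeks, in line with Section III.B.
- Apply this to continuous outcomes measured at baseline. For discrete outcomes, use the baseline value of the same measure as a covariate.
- State whether the mixed model will be run on the N=30 sample.

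Modelling the post-baseline scores with the baseline score as a covariate is a close alternative. It is not identical: it drops participants who have a baseline assessment only, which matters when the plan must "account for a conservative estimate of 30% attrition".

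The cost is a few sentences of analysis wording. No new data, visits or participants are needed.

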Aim 3: During the routine follow-up visits that are part of the Apache surveillance system, Community Mental Health Specialists (CMHSs) who complete these follow-ups may approach participants they know to be potentially eligible (based on age and behavior, two pieces of information they gather as routine part of this follow-up) to see if they are interested in hearing about this study and participating. If the potential participant is interested in hearing about the study but is unsure about participation, the CHMS will note their contact info and make a plan with the person to follow-up and continue recruitment. If the potential participant is interested in participating in the study, the CMHS will either schedule a time to complete the eligibility screening or continue by having the potential participant complete the eligibility screening questions (the eligibility screening consists of two brief screening measures, one the ACEs measure, the other a subset of questions from the Harvard Trauma Questionnaire; see data collection instruments). Once screened, if the participant is eligible based on their responses, they will complete the informed consent process. For eligible participants who consented, the CMHS will complete the initial contact form as part of the enrollment process, and either administer the rest of the baseline survey or schedule another visit to complete the baseline. After completing the baseline survey, participants will receive one snack box of approximately \$30 value. After the baseline assessment the person will be randomized to either receive My Pathway to Healing intervention immediately, in addition to case management, or to receive case management alone (standard of care) while being asked to wait for the intervention. To ensure equal distribution of certain characteristics, participants will be block randomized by index event (ideation, attempt, self-injury, or binge substance use) and gender (male or female) using a 1:1 allocation ratio within blocks. The Research Program Assistants who collect study assessments will not be blinded to the intervention allocation. Previous work with the WMAT community has taught JHCIH that it is helpful for establishing trust and promoting participation when the Research Program Assistants who collect the study assessments can work with the Research Program Assistants who deliver the interventions to communicate with the participant, instead of the participant developing two separate relationships with each an evaluator and interventionist. Additionally, the Research Program Assistants who collect the study assessments do so by preparing a mobile tablet with the survey questions and handing it to the participant to complete, as such we believe that unblinding them will not influence the assessments that are collected. Regardless of assignment, the surveillance system provides regular case management as the existing standard of care. See Figure 2 for details on participant flow.

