
Those randomized into the My Pathway to Healing (intervention) group will receive 4-8 one hour-long sessions with a community mental health specialist, taking place over 8-12 weeks. The exact number of sessions will depend on presentation and symptom level using a stepped care approach where participants receive only what they need, but the provider can provide additional sessions if needed (i.e., increased lesson dosage; additional optional lessons for specific issues). The number of sessions and the content covered will be determined using 1) the participant monitoring form (see data collection instruments) and 2) provider knowledge and evaluation of specific participant needs. The My Pathway to Healing intervention is based on modifications made to the standardized common elements intervention during Aim 2 and informed by results of Aim 1. Participants assigned to receive the MP2H intervention who are deaf or hard of hearing will be supported by sign language interpreting services provided by HIS Sign Language Interpreting, an on-demand sign language interpreting

service whose interpreters must treat all information learned during interpretation as confidential. Those randomized into the control will continue to receive the standard case management via the Apache surveillance system. These control participants will be offered the intervention after they have finished their final study assessment (approximately 6 months post-baseline) on a rolling basis based on availability of providers. After completing either the endline assessment once their intervention or control is finished, participants will receive another snack box. Finally, participants who complete the entire study (i.e., complete all 5 assessments and the intervention or control sessions) will receive a third snack box.

2. Describe the number and type of study visits and/or contacts between the study team and the participant, how long they will last, and where/how they will take place.

Aim 1: After initial contact, each study participant will be asked to engage in a maximum of two study activities—a free listing interview and an in-depth interview. The duration of study participation will last no longer than 4 hours (maximum 2hrs per study activity). All research activities will be conducted in a setting that is convenient, comfortable and private.

Aim 2: N/A

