Aim 3: Participants in the My Pathway to Healing group will receive 4-8 hour-long visits over the course of 8-12 weeks from community mental health specialists, depending on presentation and symptom level, and will receive a small journal or activity book as a token of appreciation and encouragement from their program educator after completing the My Pathway to Healing program (less than \$10 value). All visits will be completed between 8 to 12-weeks post baseline. When possible, participants homes will be used for the intervention and data collection. Additionally, all participants, regardless of group, will be asked to partake in 5 study assessments. For intervention participants these assessments will take place at: baseline, after their last session (endline; 8-12 weeks post-baseline) and 4, 8, and 12 weeks post-endline. For control participants, these assessments will take place at: baseline, 8-12 weeks post-baseline (the time the intervention would last; will be referred to as an endline) and 4, 8 and 12 weeks post-endline. These assessment visits will be conducted by separate Research Program Assistants who will serve as the independent evaluators. Assessments will take approximately 45-90 minutes to complete. See figure 2 above for an outline of study flow and visits.

3. Describe the expected duration of the study from the perspective of the individual participant and duration overall.

Aim 1: Participants will be involved in up to two interviews for a maximum duration of 4 hours (2 hours per interview). Interviews will take places within days or weeks of each other (i.e. participants will be involved in the study for a month or less).

Aim 2: NA

Aim 3: Participants will be involved in this part of the study for 6 months—up to 12 weeks of the My Pathway to Healing intervention sessions and regularly spaced assessments until 12 weeks post-end line.

4. Provide a brief data analysis plan and a description of variables to be derived.

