A schedule of assessments for study participants is included in Table 2. In addition, the CMHSs will complete session summary forms at the completion of each intervention or case management visit. All data for Aim 3 will be collected using an electronic data collection platform (REDCap). Outcomes for Aim 3 are presented in Table 2 and described below.

Frequency Measures **Outcomes** Post-Endline Baseline Endline Screening 4wks 8wks 12wks Demographics Χ Demographic questionnaire Harvard Х Posttraumatic Stress Trauma Χ Χ Χ Χ Χ Questionnaire Χ Suicide Ideation Χ Χ Χ Χ IDSS Depression Χ Χ Χ Χ ASSIST Alcohol and Substance Χ Χ Χ Χ Χ Use **Brief Grief** Χ Χ Χ Χ **Grief Experiences** Χ Questionnaire

Table 2: Schedule of Assessments for Participants (Aim 3)

Hopefulness	Trait hope scale		Х	Х	Х	Х	Х
Communal Mastery	Communal Mastery Scale		Х	Х	х	Х	Х
Functioning	WHO DAS Local Functioning Scale		Х	х	х	Х	Х
Historical Trauma	Historical Loss Scale		Х	х	х	Х	Х
Adverse Childhood Experiences	ACE module	Х					
Coping skills	Brief cope		Х	Х	х	Х	х
Self-esteem	Rosenberg self- esteem scale		Х	Х	х	Х	Х
Tribal identity	Modified leech scale to measure tribal identity		х	х	х	Х	Х
Anxiety	Hopkins symptom checklist		х	х	х	Х	х
Session summary	Session Summary Form (Control) Session summary form (intervention)	To be compl	eted with particip	ant after each curr (control) visit wit		ention) or case	management
Participant monitoring form	Questions based on items measured in baseline and curriculum content	To be completed with participant at the start of each My Pathway to Healing Visit (Only in participants assigned to this arm)					

^{*}Endline for Control Participants: 12-weeks after baseline; also the maximum length of the intervention period for Intervention *Endline for Intervention Participants: When they complete their final session, as determined by their provider Participants

Primary Outcome:

The Harvard Trauma Questionnaire is an evidence-based instrument developed to measure symptoms of trauma. Part 1 asks participants about symptoms of PTSD (a brief version of this measure is included as well in the study screening process, see data collection instruments). Part 2 asks participants about symptoms of anxiety.

Secondary Outcomes:

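### The only adverse-event field described sits on visit-triggered forms that differ by arm; the assessments both arms share list none

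*Combined protocol and SAP*

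**What the plan says.** **The form.** The session summary forms paragraph in section V.C.4 describes one version per arm. Among the contents is "what (if any) referrals were made, potential adverse events reported, interruptions during the visit", and it says that "these forms are used to track the mental health and well-being of study participants on a week-to-week basis". No other instrument in the plan is described with an adverse-event field.

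**When it is completed.** The text above Table 2 says "the CMHSs will complete session summary forms at the completion of each intervention or case management visit". The session summary row of Table 2 is broken in the text, but its sense is curriculum visits for the intervention arm and case management visits for controls. Neither place gives an end date. Table 2 has no adverse-event row at baseline, at endline, or at 4, 8 and 12 weeks after endline.

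**The visits behind it.** Intervention participants "will receive 4-8 one hour-long sessions with a community mental health specialist, taking place over 8-12 weeks" (V.C.1). Their assessments are at baseline, "after their last session (endline; 8-12 weeks post-baseline) and 4, 8, and 12 weeks post-endline" (V.C.2). For controls, V.C.1 says "Those randomized into the control will continue to receive the standard case management via the Apache surveillance system". The same section also says "After completing either the endline assessment once their intervention or control is finished, participants will receive another snack box", which treats the control condition as something that ends at endline. On case management in both arms it says "Regardless of assignment, the surveillance system provides regular case management as the existing standard of care". Control endline is 8-12 weeks in V.C.2 but 12 weeks in the note to Table 2.

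**Use of the data.** Section X.C.2 has adverse events of every type summarized for the DSMB. It gives the DSMB interim analyses covering possible harm from the programs and a judgment on whether the balance of risk and benefit has shifted. No by-arm table, common window or person-time denominator is described.

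**The concern.** Section VII.A names a specific risk of the intervention: a harmful reaction to revisiting traumatic experiences, if poorly managed. Such a reaction, or another untoward event, may come to light after the last session. If the form follows curriculum visits only, the scheduled question stops when the sessions do, and 12 weeks of follow-up remain.

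The second problem is comparability. Form-recorded events accrue only while visits occur, and the visits differ by arm in kind, number and possibly duration. A difference in counts would then mix true risk with how long and how often people were asked. With about 15 participants in the intervention arm (III.B), a few events missed or gained this way could change the safety picture behind a decision to scale up.

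**Working it through.** **Plan's own figure.** The plan states no adverse-event rate or count, so there is nothing to reproduce on this point. Its only calculated figure, the sample size in III.B (70 before and 100 after 30% attrition; 70/0.70 = 100), does not bear on it.

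**Inputs.**
- Intervention session window: 8 to 12 weeks (V.C.1).
- Follow-up after endline: 12 weeks (V.C.2), so total follow-up is 8 + 12 = 20 to 12 + 12 = 24 weeks.
- Control endline: 8-12 weeks (V.C.2) or 12 weeks (Table 2 note).
- Stop date of control forms: not stated, so each reading is worked.
- Arm size: about 15 each (N = 30, 1:1 allocation).

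**Step 1: form coverage in the intervention arm, on the Table 2 reading.** 8/20 = 40% to 12/24 = 50% of follow-up. The rest, 12/20 = 60% to 12/24 = 50%, has no scheduled adverse-event question.

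**Step 2: count ratio from collection time alone.** With equal true event rates and similar visit frequency while forms run, the expected ratio is (intervention form weeks)/(control form weeks).

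| Control forms stop at | Intervention 8 weeks | Intervention 12 weeks |
|---|---|---|
| 24 weeks (12-week endline + 12) | 8/24 = 0.33 | 12/24 = 0.50 |
| 20 weeks (8-week endline + 12) | 8/20 = 0.40 | 12/20 = 0.60 |
| 12-week endline | 8/12 = 0.67 | 12/12 = 1.00 |
| 8-week endline | 8/8 = 1.00 | 12/8 = 1.50 |

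Over these readings the ratio runs from 0.33 to 1.50, so it crosses 1. With one common window the ratio from collection time would be 1.0.

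**Step 3: the reading in which intervention participants' case management visits also trigger a form.** The time asymmetry may then disappear, but the intervention arm would generate forms from two kinds of visit while sessions run, and controls from one.

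**Step 4: visit frequency.** Sessions number 4 to 8 over 8 to 12 weeks: from 4/12 = 0.33 to 8/8 = 1 per week. Control visit frequency is not given beyond the remark on weekly tracking. The similar-frequency assumption in step 2 therefore cannot be checked.

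**Step 5: illustration with an assumed rate.** Take 0.10 events per person per 4 weeks and 15 per arm. Expected form-recorded events are 15 x 0.10 x 8/4 = 3.0 with 8 weeks of forms, 4.5 with 12 weeks and 9.0 with 24 weeks. Over an assumed range of 0.05 to 0.30, the 8-week against 24-week contrast runs from 1.5 against 4.5 to 9.0 against 27.0. All of that gap is collection time.

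**The case against.** A reader might infer that forms stop for the intervention arm, continue for controls to about 6 months, and so bias the DSMB's comparison in favor of the intervention. The documents do not support that.

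- **Control forms.** That case management continues describes a service, not how long research forms are completed. The wording in V.C.1 that the control condition finishes at endline, and the payment section's reference to completing control visits, point to forms stopping then. This stands: continuation is one reading only.
- **Intervention forms.** The sentence above Table 2 has no arm limit, and both arms receive case management. Forms might continue in the intervention arm too. This stands as a possible reading, although Table 2 and the one-form-per-arm description point the other way.
- **Other harm routes.** The suicide-ideation questionnaire (SIQ) closes every assessment in both arms (V.C.5.F, X.C.1) and is meant to pick up suicidal thoughts or acts and deterioration. Post-traumatic stress, depression and anxiety scales are repeated after endline. Staff must report events at once (X.D), and tribal surveillance captures suicidal behavior, self-injury and binge drinking (section IV). So the named harm would often show up somewhere. This stands for suicidality and symptom worsening. The scales are scores rather than event records, however, and the SIQ's past-month recall (V.C.4) does not span the 8-12 weeks from baseline to endline. None of these routes is a scheduled question about other events.
- **Direction.** The participant monitoring form, which covers safety, is used only at intervention sessions and raises detection in that arm. This stands: the net direction is unknown.
- **DSMB table.** A by-arm count is inferred from the charge to look for program harm; the plan does not state one. This stands.
- **Unseen material.** Appendix 1, the forms themselves and part of section X.A were not available, and X.C.2 refers to formal tracking procedures that the DSMB will approve. Other adverse-event items may exist.

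**Conclusion.** The point holds as a gap in harm ascertainment, not as a demonstrated bias in one direction. On every reading, the described adverse-event question is triggered by visits that differ by arm, and the assessments the arms share list no such item. On the Table 2 reading, intervention participants have no scheduled adverse-event question for the last 12 weeks, 50-60% of follow-up. If control forms also stop at endline, neither arm has one in that period, and the same remedy applies.

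The size of any distortion in form-based counts depends on a stop date the plan leaves open. The ratios in step 2 assume equal true rates and similar visit frequency, and they leave out the intervention-only monitoring form. No single ratio, and no direction, should be quoted as the effect.

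The move to a 30-person feasibility study lowers the stakes for formal comparison. It does not remove the point: sections I and III.A say that the design other than sample size stayed the same, so the monitoring plan still applies.

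**What to change.** 1. Add the existing adverse-event items from the session forms to the endline and the 4-, 8- and 12-week post-endline assessments in both arms, asking about the time since the last assessment. Add the row to Table 2.
2. Base any by-arm summary for the DSMB on these assessment counts. List session-form events and spontaneously reported events separately.
3. Reconcile the text above Table 2, the Table 2 session summary row and the two statements in V.C.1 about controls, so that the start and stop of the forms is stated for each arm. Reconcile the control endline (8-12 weeks in V.C.2, 12 weeks in the Table 2 note) at the same time.

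The cost is one table row and a few extra minutes in four assessments that already take 45-90 minutes; the items already exist on the session forms.

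The January 2025 updates describe recruitment in the past tense, so assessments may be complete. In that case, report form-recorded events per person-week of form coverage, state the coverage per arm, and limit any comparison to a window common to both arms. Weeks 0-8 fall inside the form window on every reading above. This handles collection time but not visit frequency, and it cannot recover later events that were never asked about; the report should say both.
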